# 8. Subject selection

# 8.1. Study population

The sample size will be approximately 1000 subjects who must be enrolled over the two-year period, based on the annual rate of cryoballoon ablations carried out in Spain.

All local and regional regulatory requirements must be met before the activation of each site and before the enrollment of subjects in the study. Each participating site should have the official confirmation from the sponsor authorizing them to start any study activity. Enrollment will last for 2 years. It is expected to commence in May 2016 and finish in May 2018.

A subject will be considered to be enrolled in the observational study from the moment in which he/she signs the Data Release Form for the study.

The investigator will keep a register of all the subjects enrolled in the study, linking each subject to a specific identification code for that site and that subject. This code will be assigned automatically by the electronic Case Report Form and will not contain any of the subject's personal information, so that the anonymity of the participating subjects is assured.

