## 13.1. Analysis of clinical data

It is expected to include approximately 1000 subjects enrolled at approximately 30 Spanish sites, with an enrollment period of 2 years and a follow-up period of one year from the time of enrollment of each subject. The subjects analyzed will be the ones included in the RECABA study database: "Spanish Registry of Cryoballoon Ablation". The variables analyzed will be those mentioned previously with the intention of adequately describing the activity of the clinical sites, the procedures used and the diseases treated in accordance with standard clinical practice.

All the data are anonymized in origin so that it is not possible to identify the subjects.

The collection of data will be prospective from the time of enrollment.

The database will be received codified and debugged, and the allocation of the lost values that have been decided previously.

The basic report at the end of enrollment and at the end of the follow-up period will consist of: The quantitative variables are expressed as mean, median, typical deviation and interquartile range depending on which is most suitable for the distribution of values. The differences between groups in relation to the quantitative variables will be evaluated through the student t test for independent samples or the analysis of variance (depending on the number of groups compared) and between variables through the student t test for related samples or the analysis of variance of repeated measures, as applicable. To analyze the relationships between categorical variables the chi-squared test ( $\chi^2$ ) and the Fisher's exact test will be used. The differences of proportions will be assessed through the homogeneity test  $\chi^2$ . To assess the relationships between the quantitative variables the Pearson or Spearman r correlation will be used, as appropriate.

The intermediate statistical reports proposed by the investigators will depend on the hypotheses suggested by the investigator. They will include at least a descriptive analysis such as the one described previously. In addition, the appropriate models to respond to the hypotheses proposed will be estimated, which can include techniques of the style of exploratory factor analysis, analysis of multiple contingency, analysis of logistical regression, analysis of conglomerates or analysis of multifactorial variance.

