A nominal significance of a=0.05 will be assumed for a result to be considered statistically significant. The statistical analysis will be achieved using the statistical packet SPSS 20.0.

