### **Statistical models**

In order to conclude on the primary objective of the study, the number and percentage of cases with absence of atrial fibrillation recurrences will be calculated after 12 months of follow-up, after the cryoablation procedure. The scientific coordinators of the study will have to determine the closing date of the database so that it has been possible to collect information from 12 months of follow-up of a sufficiently large number of patients.

The protocol defines AF recurrence as a clinically diagnosed and documented episode of AF (using ECG, Holter monitor with a duration of at least 30 seconds, or using implantable devices

or event monitoring systems). The information necessary to determine the existence of a recurrence of AF will be extracted from the Follow-up and Adverse Events tables.

The existence of differences between patients with and without recurrence in clinical variables and patient follow-up will be explored. Student's t statistics (for continuous variables) and  $\chi^2$  (for categorical variables) will be used. If there are appreciable differences between the groups of patients in the clinical variables, logistic regression models will be proposed to study the multivariate effect of the variables and assess their predictive capacity.

The waiting times until the moment of recurrence of AF will be described using survival models (survival tables and Kaplan-Meier) and the existence of variables capable of predicting the differences between both groups of patients will be explored.

The necessary statistical analyzes will be approached to verify the secondary objectives based on the variables designated by the study coordinators.

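### Continuous variables are to be compared between independent groups by Student's t or classical ANOVA only, so the nominal 0.05 need not hold if group sizes and spreads both differ materially.

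*SAP*

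**What the plan says.** The SAP, under Statistical models, sets up the comparison as exploration: "The existence of differences between patients with and without recurrence in clinical variables and patient follow-up will be explored". For continuous variables it names Student's "t statistics (for continuous variables" and for categorical variables the chi-squared statistic.

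Protocol section 13.1 covers group comparisons generally. Differences in quantitative variables are to be "evaluated through the student t test for independent samples or the analysis of variance", according to the number of groups, and the synopsis repeats this. The same section sets the level: "A nominal significance of a=0.05 will be assumed for a result to be considered statistically significant".

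Neither document mentions a Welch or other unequal-variance form, or a check of variances. The protocol does offer alternatives elsewhere: Pearson or Spearman for correlations, and Fisher's exact test beside chi-squared for categorical data. Comparisons of means between independent groups have no such alternative.

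The primary objective is answered separately: "the number and percentage of cases with absence of atrial fibrillation recurrences will be calculated after 12 months of follow-up".

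**The concern.** The pooled t test estimates one common variance and uses it in the standard error of both means. That is correct if the two variances are equal, and harmless in large samples if the two groups are of equal size. If neither holds, the standard error itself is wrong. It is too small when the smaller group is the more variable, and too large when it is the less variable. Adding patients does not help, because the ratio of the pooled to the true standard error depends only on the split and the SD ratio.

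Recurrence status is an outcome, so nothing in the design makes the two groups equal. The same holds for the comparisons between strata and procedures that protocol section 13 foresees. At stake is whether a reported p-value below 0.05 for a characteristic associated with recurrence means what it says. The primary result is not at stake.

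**Working it through.** **Inputs from the documents**
- Tests: Student's t or analysis of variance (SAP, Statistical models; protocol 13.1).
- Level: 0.05 (protocol 13.1). Sidedness is not stated; two-sided is assumed.
- Total size: about 1000 (protocol 13.1). Protocol 8.1 derives it from procedure volume ("based on the annual rate of cryoballoon ablations carried out in Spain"), so there is no power calculation to reproduce.

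**Inputs assumed, because the documents give none**
- p, the share of patients in the smaller group: 0.20 to 0.50 in the table below.
- k, the SD of the smaller group divided by the SD of the larger group: 0.5 to 2.

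**Formula.** Let n1 and n2 be the sizes of the smaller and larger groups, and set the larger group's SD to 1. In large samples:

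- pooled SE² = [(n1·k² + n2)/(n1 + n2)] × (1/n1 + 1/n2) = (n1·k² + n2)/(n1·n2)
- true SE² = k²/n1 + 1/n2 = (n2·k² + n1)/(n1·n2)
- R = pooled SE² / true SE² = [p·k² + (1 − p)] / [(1 − p)·k² + p]
- true type I error = 2 × P(Z > 1.96 × √R)

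The total sample size cancels out of R, which is why a large registry does not remove the problem.

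**Reproducing the nominal level.** With k = 1, R = 1 at any split and the error is 5.0%, the protocol's figure. With p = 0.5, R = 1 at any k, again 5.0%.

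**Split 250:750 (p = 0.25)**
- k = 1.5: R = (562.5 + 750)/(1687.5 + 250) = 0.677; 1.96 × 0.823 = 1.613; error 10.7%.
- k = 2: R = (1000 + 750)/(3000 + 250) = 0.538; 1.96 × 0.734 = 1.438; error 15.0%.
- k = 0.67: R = 862.2/586.7 = 1.470; 1.96 × 1.212 = 2.376; error about 1.8%.
- k = 0.5: R = 812.5/437.5 = 1.857; 1.96 × 1.363 = 2.671; error 0.8%.

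**Split 300:700 (p = 0.30) with a 10% SD difference**
- k = 1.1: R = 1063/1147 = 0.927; error 5.9%.
- k = 0.9: R = 943/867 = 1.088; error 4.1%.

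**Range over the assumptions (true type I error, nominal 5%)**

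| Split | k = 0.5 | k = 0.67 | k = 0.9 | k = 1.1 | k = 1.5 | k = 2 |
|---|---|---|---|---|---|---|
| 20:80 | 0.4% | 1.3% | 3.7% | 6.4% | 12.1% | 17.9% |
| 25:75 | 0.8% | 1.8% | 3.9% | 6.2% | 10.7% | 15.0% |
| 30:70 | 1.2% | 2.2% | 4.1% | 5.9% | 9.3% | 12.5% |
| 50:50 | 5.0% | 5.0% | 5.0% | 5.0% | 5.0% | 5.0% |

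At 40:60 the error stays between 4.1% and 6.1% for k from 0.8 to 1.25.

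**Check by simulation.** Simulation under normality, with 400,000 draws per cell, agreed with the formula for the pooled test. The Welch test gave 4.9% to 5.1% in every cell (smaller group 10% to 50% of patients, k from 0.5 to 2, total of 1000 and, as an assumed allowance for dropout, 850).

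**Price of Welch when variances are equal.** At 250:750 its degrees of freedom are (1/250 + 1/750)² / [(1/250)²/249 + (1/750)²/749] ≈ 427, against 998 for the pooled test. The critical values are 1.966 and 1.962, so the loss of power is negligible.

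**The case against.** The strongest reply is that the distortion needs two conditions together, and the documents establish neither. They give no recurrence rate, no group sizes and no SDs, and they never say in words that the variance is to be pooled. That stands. Pooling is only the usual meaning of Student's t and classical ANOVA, and the splits and SD ratios above are assumptions.

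A reader might also infer more than the documents support:

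- *That the groups are known to be very unequal, or that the error leaves 5% whenever spreads differ.* Neither follows. The error is 5% at 50:50 and close to it for small SD differences.
- *That spread rising with the mean, as is common for times and counts, causes the inflation.* It does not by itself. If spread depends on the mean, groups with equal means have similar spread, and the test stays near its level. The figures above apply where means are equal and spreads are not.
- *That the SAP makes no use of skewness and kurtosis.* They are listed as descriptive statistics, and describing shape is a use. The Welch test would not answer a complaint about shape anyway, because it still compares means.
- *That these tests decide which variables enter the models.* The SAP moves to logistic regression if differences are appreciable. It ties no p-value cut-off or selection rule to the t test.

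The reply does not remove the narrower point. The only tests named for comparing means between independent groups depend on an assumption that the plan neither checks nor needs. An alternative that holds its level in either case costs almost nothing.

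**Conclusion.** The point holds in conditional form and is minor. If group sizes and spreads both differ materially, the named tests can miss the nominal 0.05 in either direction, whatever the total sample size. At an assumed 25:75 split the error runs from 0.8% (SD ratio 0.5) to 15.0% (SD ratio 2). With mild SD differences or near-equal groups it stays close to 5%.

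The result rests on assumed splits and SD ratios, a two-sided test, and the usual pooled reading of the named tests. The comparison is exploratory, and the primary percentage without recurrence at 12 months does not use it. Nothing in the documents shows that a study conclusion would change.

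**What to change.** In protocol section 13.1 (and the matching synopsis text) and in the SAP under Statistical models, specify the Welch t test for two independent groups and Welch ANOVA for more than two, for all continuous variables. Report the mean difference with its Welch 95% interval beside the p-value. Fixing the form in advance also removes any choice between test versions after the data are seen.

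The cost is a change of wording: no new data, patients or procedures. The one downside is the negligible loss of power when the variances are in fact equal.

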#### **Baseline procedure:**

- 1.- Demographic factors, cardiovascular risk factors (arterial hypertension, diabetes mellitus, dyslipidemia, smoking), physical activity, sleep apnea, body mass index.
- 2.- Evolution time of the arrhythmia, previous anti-arrhythmic treatments, previous cardioversions.
- 3.- Anatomical data arising from the imaging tests (left ventricular parameters, ejection fraction, ventricular wall thickness, diameter, area or volume of the left atrium, pulmonary vein drainage pattern, pulmonary vein diameters)
- 4.- Procedure variables: number of applications per vein, application time, registration of pulmonary vein potentials during the ablation, time to block the vein, minimum temperature reached, reheating time, isolation or not of the pulmonary vein, results of the adenosine test, procedure time, exposure time to radioscopy, complications, temperature details in each of the applications, temperature at the time of isolation.

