## **Baseline data**

The Baseline Data table contains clinical information about the patient's situation at the baseline visit. Specifically, the date of the baseline visit, characteristics of AF, REDO, heart disease, risk factors, drugs, echocardiography, and lung anatomy.

Continuous variables will be described using the statistics of central tendency (mean and median), dispersion (minimum, maximum, standard deviation and interquartile range) and shape (skewness and kurtosis). The number of valid cases and the number of cases with missing values will be reported. The continuous variables in this table are: Date of the baseline visit, number of previous procedures, CHADS2 index, CHADS2DS2-VASc index, BMI, number of arrhythmic drugs, IVTDVI, IVTSVI and area and diameter of the LA dilatation.

The categorical variables will be described by frequencies and percentages. The number of valid cases and the number of cases with missing values will be reported. The categorical variables contained in this table are: AF type, AF evolution time, Associated arrhythmias, REDO, Type of previous procedure, Heart disease, Heart disease type, Channelopathy type, Congestive Heart Failure, Arterial hypertension, Age 65-74, Age  $\geq$  75 years, Diabetes Mellitus, Vascular disease, Female gender, History of stroke or Transient Ischemic Accident, Pacemaker carrier, Sports, Alcohol, SAHS, CPAP, Dyslipidemia, Obesity, Antiarrhythmic drugs, Type of antiarrhythmic agents, Beta-blockers, Calcium antagonists, Anticoagulants, Type anticoagulants, NACOs Type, FE, Ventricular Dilation, AI Dilation, VPI, VPI Type, VPD, VPD Type.

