## **Procedure**

The Procedure table contains technical information about the ablation procedure.

Continuous variables will be described using the statistics of central tendency (mean and median), dispersion (minimum, maximum, standard deviation and interquartile range) and shape (skewness and kurtosis). The number of valid cases and the number of cases with missing values will be reported. The continuous variables in this table are: Procedure date, TTE (sg), Minimum temperature ( $^{\circ}$ C), Application time (sg), Reheating time (sg), No. of balloons used, Total time of applications (min), Time total LA (min), Total procedure time (min), Total fluoroscopy time (min), Time to -30 degrees (sec), Rx Dose (PDA), Wait time (min), Contrast (ml), No. of cardioversions.

The categorical variables will be described by frequencies and percentages. The number of valid cases and the number of cases with missing values will be reported. The categorical variables contained in this table are: Study No., Previous Image, Image Type, Previous TEE (Transesophageal Echocardiography), General Anesthesia, Deep Sedation, Channeled Artery, No. of Diagnostic Catheters, Location of Diagnostic Catheters, Access, Assisted Transeptal, Assisted using, Phrenic nerve monitoring technique, Base rhythm, Applications, Vein, Application number, Potential visibility, Balloon size, Pulmonary vein isolation, Auriculogram, Protamine, Z-suture, Complications, Cardioversions, Number of cardioversions, Ablation ICT, Post-procedure antiarrhythmics, Antiarrhythmic type, Post-procedure anticoagulation, NACOs type, Base rhythm, Select type of Flutter, Catheter, Sheath, Specify.

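### Categorical variables with a natural order (clearly AF evolution time, probably FE) are compared by recurrence with an unordered chi-squared only; with three or more levels, a trend test beside it would recover power at almost no cost

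*SAP*

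**What the plan says.** **The comparison.** The SAP (Statistical models) sets out to explore differences between patients with and without recurrence. Continuous variables get Student's t and categorical ones chi-squared: "for categorical variables) will be used. If there are appreciable differences between the groups of patients in the clinical variables, logistic regression models" are then proposed. Protocol section 13.1 says "To analyze the relationships between categorical variables the chi-squared test" will be used, and adds Fisher's exact test. It offers Spearman's correlation, but only between quantitative variables. Neither document names a trend, rank or ordinal test for ordered categories.

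**How variables are classed.** Protocol section 9.1 collects "Evolution time of the arrhythmia, previous anti-arrhythmic treatments, previous cardioversions", and lists ejection fraction among the imaging data. The categorical list in the SAP (Baseline data) includes "AF type, AF evolution time, Associated arrhythmias, REDO" and, further on, "FE, Ventricular Dilation, AI Dilation". The categorical list in the SAP (Procedure) includes "No. of Diagnostic Catheters, Location of Diagnostic Catheters".

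**What is continuous.** The Baseline data list of continuous variables includes left atrial area and diameter, the number of previous procedures and the number of antiarrhythmic drugs. The number of cardioversions stands in both the continuous and the categorical list of the Procedure table.

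**The concern.** Pearson's chi-squared on a variable with k levels spends k−1 degrees of freedom and gives the same p-value however the levels are permuted. A steady rise in recurrence with longer AF history therefore counts for no more than the same percentages in scrambled order. A continuous variable with the same strength of association gets a 1-df t test. Duration of the arrhythmia and ventricular function are plausible graded predictors, and this step is where the SAP looks for variables related to recurrence before it proposes multivariable models. At stake is a higher chance of reporting no difference for a variable that does have a gradient.

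A smaller inconsistency needs no assumption. The cardioversion count is in both lists, so the SAP's rule assigns it both a t test and a chi-squared test.

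**Working it through.** There is no plan figure to reproduce. Neither document gives a power, effect size or recurrence rate for this comparison, and protocol section 8.1 bases the sample size on the annual number of procedures.

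**Inputs from the documents.** About 1000 subjects (protocol 8.1); nominal alpha 0.05 (protocol 13.1).

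**Assumptions.** All 1000 have an outcome; recurrence is 25%; there are k equal-sized levels; the log-odds are linear in the level, with an odds ratio of 1.2 per SD of the level score.

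**Formulas.** Level j has share w_j, score s_j and recurrence p_j; the overall recurrence is p̄.

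- Unordered chi-squared, k−1 df: λ = N Σ w_j (p_j − p̄)² / [p̄(1 − p̄)]
- Linear trend, 1 df: λ_T = N [Σ w_j (s_j − s̄)(p_j − p̄)]² / [p̄(1 − p̄) Σ w_j (s_j − s̄)²]
- Power is the probability that a noncentral chi-squared with that λ exceeds the central 95% point: 3.84, 5.99, 7.81 and 9.49 for 1, 2, 3 and 4 df.

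**Four levels.** Recurrence is 20.6%, 23.4%, 26.4% and 29.7%. The mean squared deviation from 25% is about 0.00116, so λ ≈ 1000 × 0.00116 / 0.1875 ≈ 6.2. λ_T is practically the same. The signal is equal; only the degrees of freedom differ.

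| Levels | Chi-squared | Trend | Loss (points) |
|---|---|---|---|
| 2 | 0.700 | 0.700 | 0 |
| 3 | 0.597 | 0.700 | 10 |
| 4 | 0.531 | 0.700 | 17 |
| 5 | 0.483 | 0.700 | 22 |

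A simulation of the four-level case (20,000 runs) gave 0.532 and 0.697. With N from 850 to 1000 and recurrence from 20% to 35%, the loss for 3 to 5 levels is about 9 to 22 points.

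**Varying the gradient.** Here recurrence rises linearly across equal-sized levels, with N = 1000 and mean 25%. For four levels and a 15-point spread (17.5%, 22.5%, 27.5%, 32.5%), the mean squared deviation is (0.075² + 0.025²)/2 = 0.003125, so λ = 1000 × 0.003125 / 0.1875 = 16.7.

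| Levels | 10-point spread: chi-squared / trend | 15-point spread: chi-squared / trend |
|---|---|---|
| 3 | 0.765 / 0.846 | 0.985 / 0.994 |
| 4 | 0.617 / 0.777 | 0.944 / 0.983 |
| 5 | 0.517 / 0.733 | 0.891 / 0.972 |

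The loss is about 8, 16 and 22 points for the 10-point spread and about 1, 4 and 8 for the 15-point spread. The largest 15-point loss in the range tried was at N = 800, 30% recurrence and five levels: 0.750 against 0.905, about 16 points.

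**Skewed levels.** With shares of 50, 30, 15 and 5% and recurrence of 22% rising to 34%, power is 0.570 against 0.736.

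**Where the trend test does worse** (four levels, N = 1000). A rise in the top level only (22, 22, 22, 34%) gives chi-squared 0.905 and trend 0.836. A U shape (32, 22, 22, 32%) gives 0.862 and 0.050.

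**The case against.** The strongest reply is that the documents never state the levels. Several neighbours in the Baseline data list are plainly yes/no, and a two-level variable loses nothing. This stands, and it limits the point to variables with three or more ordered levels.

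A reader might infer three stronger things that the documents do not support.

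- *That the order of atrial size and of counts in general is thrown away.* Left atrial area and diameter are already continuous, and the dilation field may be only a flag for them. The cardioversion count is also in the continuous list, and the previous-procedure and drug counts are continuous. The number of diagnostic catheters remains, but the SAP calls the Procedure table technical information while the recurrence comparison concerns clinical variables and follow-up. That count may not be compared at all.
- *That the chi-squared result decides which variables enter the logistic models.* The condition is only that differences be appreciable. It is not defined as a p-value and not applied variable by variable. Predictors are also explored alongside the survival models without that condition. The SAP is silent on how categories would be coded in any model.
- *That real gradients will be missed.* This is a loss of power, not a certainty. It is small for a strong gradient, and the trend test itself does worse for some non-monotone shapes.

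The comparison is also exploratory. What survives the objection is that AF evolution time, and probably FE, have an order, are categorical, have no direct continuous counterpart in the SAP's lists, and get only an unordered test.

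**Conclusion.** The point holds in a limited form and is minor: a cheap improvement. For ordered variables held only as categories, with three or more levels, the stated test gives up power against a monotone gradient. The size is about 10, 17 and 22 points with 3, 4 and 5 levels under an odds ratio of 1.2 per SD, and about 1 to 8 points for a 15-point gradient, both at N = 1000 and 25% recurrence. These figures rest on assumed recurrence, effect size, level sizes and linearity. The primary result, a number and percentage free of recurrence, does not depend on this step. The double listing of the cardioversion count is an inconsistency whatever is assumed.

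**What to change.** In the SAP (Statistical models) and protocol section 13.1, add wording such as:

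> Categorical variables with three or more ordered levels will also be compared between patients with and without recurrence by the chi-squared test for linear trend (linear-by-linear association). The unordered chi-squared test will be shown beside it to reveal non-monotone patterns. In logistic models these variables may enter as ordered scores after a check of linearity.

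State the levels of AF evolution time and FE, so that it is clear which variables this covers. Linear scores should not be fixed in the models before levels and spacing are known. In the SAP (Procedure), list the number of cardioversions once, as a count.

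**Cost.** Wording only: no new data, and linear-by-linear association is a standard SPSS crosstab statistic. The downside is one more exploratory p-value per ordered variable. The trend test's lower sensitivity to non-monotone patterns is covered by keeping the unordered test.
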